4 STUDY DESIGN

This is a phase IV, non-randomized, multicenter study involving at least 50 evaluable subjects diagnosed with severe hemophilia A (levels of Factor VIII:C in plasma less than 0.01 IU/mL), who are male, at least six years of age and not more than 65 years of age, and with a Karnofsky Performance Score of at least 50. All subjects will have adequate immune system function (CD4 count must be greater than or equal to 400 cells/µL and subject must not have an immune system impairment or damage by disease or treatment).

Contains Confidential and Proprietary Information of Grifols Inc.

Enrolled subjects will be treated at home and with in-clinic therapy exclusively with Alphanate[®] as their sole source of FVIII concentrate for prophylaxis and treatment of all bleeding episodes and surgical procedures for a period of at least two years and a minimum of 50 exposure days, or, if 50 exposure days are not reached, for a maximum of 30 months. Alphanate[®] will be administered in accordance with the subject's usual pre-study treatment regimen. An exposure day is defined as any day on which a subject receives one or more infusions of any Factor VIII containing product. However, only one exposure day will be accrued for each surgical episode, regardless of the number of days of treatment or the number of infusions of Factor VIII associated with that surgical procedure.

A subject will continue treatment, as specified above, unless

- The subject develops inhibitors to Factor VIII at a titer greater than or equal to 5 Bethesda units (BU/mL);
- treatment with Factor VIII becomes ineffective at providing hemostasis even for a subject who has developed inhibitors with a titer of less than 5 BU/mL; or
- the subject exhibits severe or serious adverse events that prevent completion of participation in the study.

In all instances, only the inhibitor titer obtained by the central reference laboratory will be used to determine the subject's eligibility to continue his participation in the trial.

The primary endpoint of this study is:

the incidence of Factor VIII inhibitor after exposure to Alphanate[®].

The secondary endpoints are:

1. The frequency, nature, causality and severity of adverse events.
2. The occurrence of changes in biochemical parameters which would indicate alterations in renal or hepatic function.

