7.8 Miscellaneous

All enrollment tests should be performed prior to the first administration of Alphanate®. Samples drawn for quarterly testing will be drawn \pm 10 days of the scheduled visit date. The presence of inhibitors will be determined by the Nijmegen modification of the Bethesda assay (see below); the Factor VIII source for this assay will be normal pooled plasma. **Inhibitor titers will be considered valid if the subject's Factor VIII level is at or below baseline (less than 0.01 IU/mL)**, therefore, the subject should be scheduled for the quarterly visit at least three days after an infusion with Alphanate®.

If the subject's Factor VIII levels are higher than baseline at the time the plasma sample is drawn, then the subject will be rescheduled for testing within one week of the notification of the invalid result.

Assays for inhibitor to Factor VIII will be performed locally (i.e., at the coagulation testing laboratory for each clinical site) to support decisions regarding treatment. Duplicate plasma samples will be collected at each time point for confirmatory testing at a central reference laboratory. The central laboratory will utilize the Nijmegen modification of the Bethesda assay to improve reliability.¹⁷ The modification involves the following changes in reagents: (1) buffering of the normal pooled plasma used in the assay and control with 0.1 M imidazole to pH 7.4 and (2) replacing the imidazole buffer in the control mixture with immunodepleted Factor VIII-deficient plasma. In addition, to further improve the accuracy of the assays, a standardized immunodepleted plasma will be used for the performance of the assay at all clinical sites, as well as at the central reference laboratory.

The local laboratories will not be required to test for Factor VIII inhibitors using the Nijmegen modification of the Bethesda assay, but are required to provide the sponsor with a detailed description of the procedure used.

Contains Confidential and Proprietary Information of Grifols Inc.

Only the results of the assays from the central reference laboratory will be used in the determination and analysis of the primary endpoint for the clinical trial.

To determine the risk of transmission of parvovirus B19, subjects who are seronegative at enrollment will be tested approximately one week after receiving the first infusion with Alphanate[®] for the presence of parvovirus B19 by Polymerase Chain Reaction (PCR) testing.

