Surgery requires that the Factor VIII level be raised to 0.50 to 0.80 IU/mL with the level maintained at or above 0.30 IU/mL for approximately two weeks postoperatively. For dental extractions, the Factor VIII level should be raised to 0.50 IU/mL immediately prior to the procedure; further Factor VIII may be given if bleeding recurs.²⁰

In subjects who experience frequent hemorrhages, Antihemophilic Factor (Human), Alphanate®, may be administered prophylactically on a daily or every other day schedule to raise the Factor VIII level to approximately 0.15 IU/mL.²¹

In pediatric subjects, no clinical trials for safety and effectiveness have been conducted in 16 years of age or younger. Across well-controlled half-life and recovery clinical trials in patients previously treated with Factor VIII concentrates for Hemophilia A, the one pediatric subject receiving Alphanate® (Solvent/Detergent) responded similarly when compared with 12 adult subjects.²²

Contains Confidential and Proprietary Information of Grifols Inc.

Factor VIII levels should be monitored periodically to evaluate the response of individual patients to a given dosage regime.

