APPENDIX 2: SCHEDULE OF EVENTS

Test	Screening ¹	Enrollment ²	Seven to 14 days Post Infusion 1	In Hospital and In Clinic Treatments	Every Three Months until Month 30 and/or Off-Study ³	Unsched
Sign Informed Consent Form	X					
Physical Examination medical & past treatment history, vital signs, height & weight	X					
Abbreviated Physical Exam interim medical history, vital signs, & weight		X			X	X
Hematology Panel CBC with WBC differential and platelet count	X				X	X
Biochemistry Panel ALT, AST, AP, LDH, BUN, total bilirubin, and creatinine	X				X	X
Viral Serology HBsAg, and antibodies to HAV, HBcAb, HBsAb, HCV, HIV1/HIV-2, and parvovirus B19 (by routine immunoassay)	X	X ²			X	X ⁵
Parvovirus B19 PCR Assay performed only if seronegative for parvo B19 at enrollment			X			
CD4 Count	X					
Factor VIII:C	X	X ²			X	X
Factor VIII:C Inhibitor (two sets of samples)	X	X ²			X ⁴	X ^{6,7}
Collect 2 mL citrated plasma for inhibitor testing			X			
Plasma for inhibitor characterization ⁷ performed only if subject develops an inhibitor					X ⁷	
Serum for storage Draw approx 5 mL of serum and aliquot into three vials of at least 1.5 mL of sample each. Freeze and retain the sample at -20°C for later serological & virological tests.	X	X			X	X
Patient Diary if the Alphanate® is to be self-administered			X	X	X	X
Physician's Assessment of Hemostasis evaluated as "None," "Moderate," "Good," or "Excellent"				X		

1. Perform at least 72 hours after the most recent administration of any F VIII conc. or any other blood products.
2. These tests are to be performed at enrollment (baseline testing) only if the subject received any Factor VIII, cryoprecipitate, or whole product treatment *after* screening tests were performed.
3. Quarterly testing will be \pm 10 days of scheduled testing date. Schedule the visit at least three days after an infusion with Alphanate®.
4. If subject develops an inhibitor, repeat assay at two week intervals until either the inhibitor falls to < 0.6 BU/mL or it is clear that the inhibitor titer will not fall.
5. Perform only if subject exhibits clinical or subjective symptoms indicating possible viral infection.
6. Perform only if a) there is a clinical indication that the normal dosage of Alphanate® is not providing adequate hemostasis or b) surgery.

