7. DATA HANDLING METHODS

7.1 Missing Data

Every effort will be made to obtain required data at each scheduled evaluation from all patients who have been enrolled. There will be no imputation for missing data.

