9. STATISTICAL ANALYSIS

9.1 Primary Analysis

Analysis of the primary safety endpoint will be conducted on the Safety Population. The primary safety endpoint, presence/absence of Factor VIII inhibitors, will be summarized with frequencies and percentages.

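### Inhibitor titres are valid only with Factor VIII below 0.01 IU/mL, permitted frequent prophylaxis may prevent that, and the SAP has no rule for subjects without a valid titre

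*Protocol*

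**What the plan says.** Protocol Section 7.8 sets one validity condition for a titre: "Inhibitor titers will be considered valid if the subject's Factor VIII level is at or below baseline (less than 0.01 IU/mL". From that it derives a scheduling instruction, that "the subject should be scheduled for the quarterly visit at least three days after an infusion with Alphanate". The schedules of events (Protocol Appendix 2, SAP Section 3.2) repeat it: "Schedule the visit at least three days after an infusion with Alphanate". A subject whose sample fails the level is to be "rescheduled for testing within one week of the notification of the invalid result". What happens if the repeat fails too is not stated.

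On treatment, Section 4 has Alphanate "administered in accordance with the subject's usual pre-study treatment regimen". Section 7.9.1 lists routine prophylaxis among the indications. Section 7.9.2 says that for subjects who bleed often the product "may be administered prophylactically on a daily or every other day schedule", aiming at about 0.15 IU/mL.

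Section 8.1 makes a subject evaluable for the primary endpoint once he has 50 exposure days on Alphanate or an inhibitor of 5 BU/mL or more. A valid titre is not required.

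The SAP analyses the primary endpoint in the Safety Population, from which Section 5.1 drops no treated subject. Section 9.1 states that "presence/absence of Factor VIII inhibitors, will be summarized with frequencies and percentages". Section 7.1 adds: "There will be no imputation for missing data". The SAP contains no validity rule, no minimum number of valid titres, and no category for subjects who cannot be assessed.

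**The concern.** The sampling text and the prophylaxis text are not cross-referenced. A subject who stays on daily or every-other-day infusions never has a three-day gap, and retesting him within a week meets the same obstacle. The subjects with most exposure, who tell most about immunogenicity, are then the ones least likely to yield a valid titre.

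Nothing later in the plan catches this. At one infusion every other day, 50 exposure days take about 50 × 2 = 100 days, so a subject can become evaluable under Section 8.1 without ever having been validly tested. If the SAP's two-level summary then leaves him among those without an inhibitor, reported incidence is too low. Protocol Section 9.2.1 and SAP Section 4 let a single inhibitor in 50 subjects decide whether incidence is judged too high, so one missed case can change the conclusion.

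**Working it through.** **The plan's own figure.** The only precision statement (Protocol 9.2.1, SAP 4) is that the one-sided 95% interval for 50 subjects reaches two percent. That is not reproduced. The exact one-sided upper limit is 5.8% for 0/50 and 9.1% for 1/50; two percent matches only the point estimate 1/50. This is a separate matter and does not decide the present point.

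**Step 1: the interval.** The permitted dosing intervals are 24 h and 48 h; the scheduling instruction asks for 72 h. Both are shorter, so no visit on an uninterrupted schedule complies. Moving the visit within the ±10-day window does not change the gap between infusions.

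**Step 2: the level.** The target after a prophylactic dose is about 0.15 IU/mL and the validity limit is 0.01 IU/mL. The fall takes log2(0.15/0.01) = log2(15) = 3.91 half-lives. The documents give no half-life h, so I assume 8 to 18 h with first-order decay.

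- Single dose: C(t) = 0.15 × 2^(−t/h)
- Steady-state trough, interval τ: 0.15 × 2^(−τ/h) / (1 − 2^(−τ/h))

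| Time after dose | Single dose, h = 8 to 18 h (IU/mL) | Below 0.01? |
|---|---|---|
| 24 h | 0.019 to 0.060 | never in this range |
| 48 h | 0.0023 to 0.024 | only if h < 48/3.91 = 12.3 h |
| 72 h | 0.0003 to 0.0094 | yes |

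Steady-state troughs are 0.021 to 0.099 IU/mL on daily dosing and 0.0024 to 0.028 on every-other-day dosing, the latter below 0.01 only if h is under about 12 h. Under these assumptions daily dosing fails both the interval and the level. Every-other-day dosing fails the interval but meets the level in some subjects.

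**Step 3: effect if untested subjects are counted as absent.** Let p = 3%, the plan's assumed maximum rate (its word is biannual, read here as two-year), and let m be the share without a valid titre. The documents do not give m. Assume equal risk in tested and untested subjects. Expected reported incidence is p(1 − m), and the chance of seeing at least one inhibitor in 50 is 1 − [1 − p(1 − m)]^50.

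| m (assumed) | Expected reported incidence | P(≥1 in 50) | P(≥2 in 80) |
|---|---|---|---|
| 0% | 3.0% | 78.2% | 69.6% |
| 10% | 2.7% | 74.6% | 64.0% |
| 20% | 2.4% | 70.3% | 57.5% |
| 30% | 2.1% | 65.4% | 50.3% |
| 50% | 1.5% | 53.0% | 33.8% |

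The last column is the binomial tail for the plan's 80-subject rule, which tolerates no more than one case.

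**Step 4: precision if only validly tested subjects count.** With zero cases the exact one-sided 95% upper limit is 1 − 0.05^(1/n).

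- n = 50: 5.8%
- n = 35 (50 × 0.7): 8.2%
- n = 25 (50 × 0.5): 11.3%

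**The case against.** The prophylaxis wording is permissive, sits in a dosing guide, and concerns only subjects with frequent hemorrhages. Inclusion criterion 5 and Section 7.1 already require 72 hours without Factor VIII before screening, so the protocol expects such a gap to be achievable in this population. To be unassessable, a subject would need every quarterly titre and every repeat to be invalid over two years or more. Section 7.5 adds inhibitor testing when hemostasis is inadequate or surgery occurs. The SAP refers to the protocol for conduct, and its tables and listings would show the Factor VIII and inhibitor results.

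Much of this stands. It limits the conflict to schedules that are not interrupted for sampling, and it makes a large unassessable share uncertain. It does not close the gap: no passage says that prophylaxis is to be interrupted for quarterly sampling, a second invalid result has no rule, and listings do not define a denominator.

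Three stronger readings are tempting and are not supported:

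- A reader might infer that a titre counts only when three days have passed. The validity condition is the Factor VIII level; the three days is a scheduling instruction, and an earlier sample below 0.01 IU/mL is valid under the text.
- A reader might infer that the SAP will report untested subjects as inhibitor-free. It does not say so. With no imputation they could equally be shown as missing.
- A reader might infer that the SAP will present the 50-subject upper limit whatever the number tested. Section 9.1 plans no confidence interval at all.

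**Conclusion.** The point holds in a limited form. The sampling instruction and the permitted daily or every-other-day prophylaxis cannot both be followed on an uninterrupted schedule, and the passages must be reconciled. The SAP omits the protocol's validity rule and leaves the classification of subjects without a valid titre undefined, although the primary endpoint is reported over all treated subjects. Counting such subjects as absent is one possible outcome and would bias incidence downward.

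The size is unknown, because the documents give neither the share of subjects on such schedules nor the share that would lack every valid titre. The figures above are illustrations. They rest on assumed shares of up to 50%, on reading the 3% rate as two-year, and on equal risk in tested and untested subjects; the statement about the level also rests on an assumed half-life. A change is still worth making, because the plan's decision rule turns on one case in 50 and the remedy is cheap.

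**What to change.** **Protocol.** The sponsor should reconcile Sections 4, 7.8, 7.9.1 and 7.9.2 with the schedules of events, and state how a repeat sample that is also invalid is handled. Which passage should give way is a clinical decision; no dosing or clinical rule is proposed here.

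**SAP Section 9.1.**

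- Carry over the validity rule, using the central Factor VIII:C paired with each central titre. Section 7.4 already draws Factor VIII:C each quarter but does not name the laboratory, so the SAP should.
- Count a subject as *present* if he has any confirmed inhibitor.
- Count him as *absent* only if he has at least one valid negative central titre after baseline and no confirmed inhibitor.
- Report everyone else as *not assessable*, and tabulate valid titres per subject.
- Show incidence for the assessable subjects and for the full Safety Population, each with an exact confidence interval. State whether it is one-sided, as in SAP Section 4, or two-sided, as in SAP Section 6.5.

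The sample at seven to fourteen days has no scheduled Factor VIII:C, so without one it cannot count as a valid negative.

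**Cost.** A protocol clarification, some SAP wording and one added table. Validity at quarterly visits can be derived from scheduled tests, provided central Factor VIII:C values exist. The downside is a smaller assessable denominator and a wider interval.

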7.9 Administration of Alphanate[®]

7.9.1 Product usage and subject diaries

Alphanate[®] will be administered as needed during the study. Indications for infusion include:

- bleeding episode or hemorrhage;
- routine prophylaxis;
- prophylactic treatment prior to physiotherapy or surgery.

Following enrollment, the subject will have the choice of obtaining Alphanate[®] treatment at the participating study site in response to bleeding episodes, or to receive treatment at home. If the Alphanate[®] is to be self-administered, then the subject must maintain an infusion diary, which will contain the following information:

- date of infusion;
- number of units infused;
- number of vials used;
- lot number(s);
- reason for infusion;
- any adverse events

The site should provide the subject with adequate drug supply for three months based on the subject's anticipated needs.

7.9.2 Alphanate[®] dosing guidelines

All subjects will be infused with the appropriate dose of Alphanate[®] (as determined by the investigator) for the prevention and/or control of bleeding, as needed. The dose and duration of therapy with Alphanate[®] will depend on the severity of the Factor VIII deficiency, the location and extent of the bleeding and the individual's physical condition. The amount of coagulation factor administered and the frequency of dosing will always take into account the clinical effectiveness of the product in each individual. However, the

Contains Confidential and Proprietary Information of Grifols Inc.

following regimen should be used as a guide for dosage calculation in the treatment of adults with hemophilia A.

Antihemophilic factor (Factor VIII:C activity) potency is expressed in International Units (IU) on the product label, where one unit approximates the activity in one milliliter of normal plasma. Replacement therapy studies have shown a linear dose-response relationship, with a 2.0-2.5 % increase (0.020-0.025 IU/mL) in Factor VIII activity for each unit of Factor VIII:C per kg of body weight transfused, from which an approximate factor of 0.5 IU/kg can be calculated.^{18, 19}

The following formula provides a guide for dosage calculation (the plasma Factor VIII may vary depending upon the age, weight, severity of hemorrhage, or surgical procedure of the subject):

$$\begin{aligned} \text{Number of Factor VIII:C Required} = \\ \text{Body Weight (kg)} \times 0.50 \text{ (IU/kg)} \times \text{Factor VIII:C Desired Increase (percent)} \end{aligned}$$

For example, in order to increase the Factor VIII:C concentration to 30 percent in a subject with a body weight of 50 kg, the formula is applied as follows:

$$50 \text{ kg} \times 0.50 \text{ IU/kg} \times 0.30 \text{ IU/mL} \times 100 = 750 \text{ IU Factor VIII:C}$$

Mild to moderate hemorrhages may usually be treated with a single administration sufficient to raise the plasma Factor VIII level to 0.20 to 0.30 IU/mL. In more serious hemorrhages, the subject's plasma Factor VIII level should be raised to 0.3 to 0.5 IU/mL. Infusions are generally required at twice daily intervals over several days.¹⁹

Surgery requires that the Factor VIII level be raised to 0.50 to 0.80 IU/mL with the level maintained at or above 0.30 IU/mL for approximately two weeks postoperatively. For dental extractions, the Factor VIII level should be raised to 0.50 IU/mL immediately prior to the procedure; further Factor VIII may be given if bleeding recurs.²⁰

In subjects who experience frequent hemorrhages, Antihemophilic Factor (Human), Alphanate®, may be administered prophylactically on a daily or every other day schedule to raise the Factor VIII level to approximately 0.15 IU/mL.²¹

In pediatric subjects, no clinical trials for safety and effectiveness have been conducted in 16 years of age or younger. Across well-controlled half-life and recovery clinical trials in patients previously treated with Factor VIII concentrates for Hemophilia A, the one pediatric subject receiving Alphanate® (Solvent/Detergent) responded similarly when compared with 12 adult subjects.²²

Contains Confidential and Proprietary Information of Grifols Inc.

Factor VIII levels should be monitored periodically to evaluate the response of individual patients to a given dosage regime.

7.10 Quarterly Clinic/Office Visits

Each participating subject will return to the study site at least quarterly for examination and collection of his infusion diary and for his quarterly drug supply. At each visit, the subject will bring all used and unused containers of Alphanate®, in addition to the diary. During the quarterly visits an abbreviated physical examination will be performed by the investigator or a staff member designated by the investigator. Blood samples will be collected for required testing, and the usage of the study drug, prescription medication and blood products will be determined. At each visit, the study nurse will discuss the information in the diary with the subject and will reconcile drug use. A new diary and a new supply of Alphanate® will be given to the subject.

Participating sites will:

- maintain these diaries in the subject files as part of the case report forms;
- verify, to the extent possible, their accuracy by comparing Alphanate® usage in these diaries against their own prescription information; and
- discuss with the subject any adverse events and their severity.

7.11 Subjects Who Develop Inhibitors

If at any quarterly visit, the subject tests positive for the presence of Factor VIII inhibitors, (inhibitor titer of 0.6 modified BU/mL or greater) based on the local lab test and confirmed by the central reference laboratory test result, the following steps should be taken:

- For an inhibitor titer of greater than or equal to 10 BU/mL,
 - Collect a 10 mL sample of citrated plasma and send to the central reference laboratory.
 - Withdraw the subject only after performing all required testing (see Section 7.4) and only after receiving confirmation of the inhibitor titer from the central reference laboratory.
- For an inhibitor titer less than 10 BU/mL,

Contains Confidential and Proprietary Information of Grifols Inc.

- Collect a 50 mL sample of citrated plasma. This sample can be obtained in multiple draws within a two-week period and sent to the central reference laboratory.
- Repeat inhibitor titer assay at two-week intervals until:
 1. the inhibitor titer decreases to < 0.6 modified BU/mL or
 2. the subject's participation in the study is ended or
 3. it becomes apparent that, after repeated assays at two-week intervals, the inhibitor titer will not decrease during the course of the study (the investigator should first consult with the Project Manager prior to making this determination).
 - If the subject's inhibitor level is less than 5 BU/mL and treatment with Alphanate® at higher doses remains effective in achieving hemostasis, then the subject will continue the current treatment regimen and testing will be performed as described in Section 7.4 above.
 - If Alphanate® treatment either becomes ineffective in achieving hemostasis, even if the inhibitor titer remains below 5 BU/mL, or if the inhibitor level rises to greater than or equal to 5 BU/mL, as confirmed by test results from the central reference laboratory, then the subject will be withdrawn from the study.

Subjects withdrawn from the study may either be treated with alternate concentrates or commence a treatment program with Alphanate® for the induction of immune tolerance. The treating physician, in consultation with Grifols Office of Medical Affairs, will determine the alternate treatment or product and the immune tolerance protocol.

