7.4 Every 3 Months until Month 30 and/or Off-Study

Samples for quarterly testing will be drawn \pm **10 days** of the scheduled visit date. At each of these visits, the following procedures will be performed:

1. Abbreviated physical examination including: interim medical history, vital signs (pulse, respiratory rate, oral temperature, blood pressure) and weight;
2. Factor VIII coagulant activity (Factor VIII:C);
3. Factor VIII inhibitor levels (BU/mL) in two sets of samples;
4. Hematologic status will be assessed by: complete blood count (CBC) with white blood cell (WBC) differential and platelet count.
5. Serum chemistry tests including: alanine aminotransferase (ALT), aspartic aminotransferase (AST), alkaline phosphatase (AP), lactic acid dehydrogenase (LDH), blood urea nitrogen (BUN), creatinine and total bilirubin;
6. Viral and serological tests including: testing for HBsAg, and for antibodies to HAV, HBcAb, HBsAb, HCV, HIV-1/HIV-2 (only if seronegative at baseline) and parvovirus B19 by routine immunoassay (only in subjects who are seronegative at baseline);
7. A sample of venous blood will be drawn from which approximately 5 mL of serum will be prepared and aliquoted into three vials of at least 1.5 mL of sample each. The samples will be frozen and retained at -20°C in the event that they are required for later serological or virology tests.

If at any quarterly visit, **the subject tests positive for the presence of Factor VIII inhibitors (inhibitor titer of greater than 0.6 modified BU/mL), based upon the value determined by the central reference laboratory**, the procedures specified in section 7.12 (Subjects Who Develop Inhibitors) will also be performed.

Contains Confidential and Proprietary Information of Grifols Inc.

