9.2 Planned Method of Analysis

9.2.1 Primary Endpoint

Incidence of Antibody Inhibitors to Factor VIII in Individuals Treated with Alphanate[®]

Assuming a maximum biannual rate of inhibitor incidence of three percent in multi-transfused hemophilia patients, the 95% one-sided confidence interval for this incidence rate in a sample of 50 subjects is up to two percent. Thus,

Contains Confidential and Proprietary Information of Grifols Inc.

with a sample of 50 evaluable subjects monitored for two years, if one subject develops an antibody inhibitor to Factor VIII with a titer higher than 0.6 modified BU/mL, that persists for at least one month, the incidence of inhibitors to Factor VIII will be judged to be higher than that for patients with hemophilia A who are treated with currently marketed Factor VIII concentrates. If the sample size is increased to 80 subjects, no more than 1 subject may develop an antibody inhibitor to Factor VIII.

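### Protocol 7.11 starts inhibitor follow-up on a different cut-off and laboratory condition from 7.4 and 7.5, so the one-month persistence that 9.2.1 requires may go unobserved or be read two ways

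*Protocol*

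**What the plan says.** Five places bear on what counts as a positive inhibitor test and what follows from it.

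- **Protocol 7.11** holds the follow-up steps. It applies them at a quarterly visit to an "inhibitor titer of 0.6 modified BU/mL or greater) based on the local lab test and confirmed by the central reference laboratory test result". Below 10 BU/mL the steps include repeat assays every two weeks, and one reason for ending them is that "the inhibitor titer decreases to < 0.6 modified BU/mL".
- **Protocol 7.4** (quarterly) and **7.5** (unscheduled) call for those steps at an "inhibitor titer of greater than 0.6 modified BU/mL), based upon the value determined by the central reference laboratory". Both send the reader to Section 7.12 under the title that belongs to 7.11; the actual 7.12 deals with other blood products.
- **Protocol 7.8** says: "Only the results of the assays from the central reference laboratory will be used in the determination and analysis of the primary endpoint". It also says: "The local laboratories will not be required to test for Factor VIII inhibitors using the Nijmegen modification".
- **Protocol 9.2.1** judges the incidence too high if one of 50 evaluable subjects "develops an antibody inhibitor to Factor VIII with a titer higher than 0.6 modified BU/mL, that persists for at least one month". SAP 4 repeats this sentence.
- **SAP 9.1** says only that the endpoint, "presence/absence of Factor VIII inhibitors, will be summarized with frequencies and percentages". It names no cut-off, laboratory or persistence condition. Protocol 8.1 gives no counting titer either; its 5 BU/mL figure concerns who is evaluable.

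**The concern.** The follow-up section and the sections that point to it disagree on three things: the sign at 0.6, whether a local positive is needed, and which visits are covered. This matters because the event in 9.2.1 is defined by duration. Central results can show duration only if a second sample is drawn at the right time, and 7.11 is the section that schedules those samples.

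If 7.11 is read as the operative rule, the local assay, which need not be the Nijmegen method, decides whether the repeats start. The sign at 0.6 matters when the titer falls back to the boundary and someone must decide whether the inhibitor persisted. With 50 subjects the acceptable count is zero, so a single subject whose persistence is unobserved or disputed can change the stated conclusion.

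**Working it through.** The plan has no figure of its own on this point, so the check is mainly a comparison of texts. The one number tied to the event count, an upper limit of two percent in 50 subjects, is a separate matter and is not used below.

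**Step 1. The rules side by side** (L = local titer, C = central titer, in BU/mL)

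| Place | Condition | Visits |
|---|---|---|
| Protocol 7.4 | C > 0.6 | quarterly |
| Protocol 7.5 | C > 0.6 | unscheduled |
| Protocol 7.11 | L ≥ 0.6 and C ≥ 0.6 | quarterly only |
| Protocol 9.2.1 with 7.8; SAP 4 | C > 0.6, lasting at least one month | not stated |
| SAP 9.1 | none given | not stated |

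The sample at 7 to 14 days (Protocol 7.3) is sent for central inhibitor testing, and none of the three triggers names that visit.

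**Step 2. Illustrative pairs of titers put through each rule**

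| L | C | 7.4 / 7.5 positive | 7.11 positive | Above the 9.2.1 cut-off |
|---|---|---|---|---|
| 0.7 | 0.7 | yes | yes | yes |
| 0.5 | 0.7 | yes | **no** | yes |
| 0.7 | 0.6 | no | **yes** | no |
| 0.6 | 0.6 | no | **yes** | no |
| 0.7 | 0.5 | no | no | no |

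The second row is the laboratory conflict. The third and fourth are the cut-off conflict, which arises only at a central value of exactly 0.6.

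**Step 3. What the missing repeats can hide.** Take three months as 91 days and one month as 30 days, and count from the first positive sample (the documents give no central turnaround time).

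- Two-weekly repeats fall on days 14, 28 and 42. The first one at or beyond 30 days is day 42.
- With each quarterly visit allowed 10 days either way, the next quarterly sample falls between 91 − 20 = 71 and 91 + 20 = 111 days.
- So an inhibitor still present on day 42 but gone by the next visit would be shown to last a month under the repeat schedule and not under quarterly sampling alone. The exposed interval is 71 − 42 = 29 to 111 − 42 = 69 days.
- An inhibitor first found at the last visit has no later quarterly sample. The repeats do not clearly cover it either, because 7.11 also ends them when participation ends.

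**Step 4. Persistence at the boundary.** Suppose the central titer is 0.8 and then 0.6 a month later. Under 7.11 the inhibitor is still present, since 0.6 is not below 0.6. Under 9.2.1 the second value is not above the cut-off. Because 9.2.1 does not say whether the inhibitor or the titer above 0.6 must last the month, the same two results can be read either way.

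**Step 5. How often one case is decisive.** With 50 subjects, P(exactly 1 case) = P(≥ 1) − P(≥ 2).

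- At the plan's assumed maximum of 3%, taken as a two-year rate: 0.782 − 0.445 = 0.337.
- At 8 per 1,000 patient-years (the previously-treated cohort in Protocol 1) over two years, 2 × 0.8% = 1.6%: 0.554 − 0.191 = 0.363.

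In about a third of such trials the 9.2.1 judgement would rest on one subject. This measures how much one case matters. It says nothing about how often a case would be missed.

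**The case against.** The strongest reply is that the endpoint is better protected than 7.11 suggests.

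- 9.2.1 and SAP 4 state the same counting rule, and 7.8 assigns the endpoint to the central laboratory. 7.11 is a procedure and does not define the endpoint.
- 7.4 and 7.5 order the follow-up on the central value alone. Footnote 4 of the schedule (Protocol Appendix 2, repeated in SAP 3.2) calls for two-weekly repeats once an inhibitor develops and sets no local condition.
- Quarterly testing continues, so two successive central positives would show persistence without any two-weekly repeat.
- At the boundary, 7.11 is the more inclusive entry rule, so its sign alone withholds follow-up from no one whom 7.4 would include.
- 7.8 provides a standardized deficient plasma for the assay at all sites, which should reduce disagreement between laboratories.

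All of this stands, and it rules out three stronger readings that a reader might infer. One sample cannot be an event under one section and a non-event under another, because 9.2.1 always requires a month's duration. A central-positive, local-negative case is not necessarily lost, because a site may follow 7.4 or the next quarterly sample may still be positive. And one misread sample does not by itself decide the trial. Nor can a percentage of missed cases be given, because the documents contain no sensitivity figure for the local assays.

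The reply does not remove the conflict. No passage ranks 7.4 and 7.5 above 7.11, and a site that follows them arrives, through a wrong section number, at a section with a different entry condition. Footnote 4 names neither a starting titer nor a laboratory. The rule in 7.8 governs which results are analysed, not which samples are drawn.

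**Conclusion.** The point holds in a limited form: the trigger in Protocol 7.11 is wrong as written against 7.4, 7.5 and 7.8. The local condition does not decide an event. If 7.11 is followed, however, it withholds the two-weekly repeats from a central-positive, local-negative subject. The exposed cases are an inhibitor that lasts over a month but clears before the next quarterly sample, and one first found at the last visit. Separately, whether an inhibitor that falls to exactly 0.6 has persisted is unclear, and neither Protocol 8.1 nor SAP 9.1 settles it.

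The textual conflict is certain. Its frequency is unknown, because it depends on how often the laboratories disagree, how long low-titer inhibitors last and which section each site follows. The consequence is bounded by the decision rule: one case changes the judgement at 50 subjects, and a second does so at 80. The day counts rest on the month lengths assumed above and on repeats running from the first positive sample.

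**What to change.** 1. State one cut-off, with the same sign, in Protocol 7.4, 7.5, 7.11 (start and end of repeats) and 9.2.1, and in SAP 4 and SAP 9.1. Which sign to use is the sponsor's decision.
2. In 7.11, trigger the repeat titers needed for the endpoint on the central result, whatever the local result and whatever the visit, including unscheduled visits and the 7 to 14 day sample. This follows what 7.4, 7.5 and 7.8 already imply. Give footnote 4 of both schedules the same trigger.
3. In 9.2.1 and SAP 9.1, name the central laboratory, say which results establish one month's persistence, and say how an inhibitor first found at the last visit is confirmed or counted.
4. Correct the reference to Section 7.12 in 7.4 and 7.5.

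None of this needs to alter the treatment or withdrawal rules, which remain with the sponsor. The cost is wording in both documents and a few extra repeat titers.
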